- Implementation and economic domains include human resources for integrating mental health care within the HIV clinic (implementation officer, peer supervision, clinic staff advisory team), treatment protocol adherence (a random 20% of IPT sessions are externally reviewed for IPT adherence), repeated stakeholder engagement (local and national) and a detailed economics core assessing patient-level benefits, formal and informal productivity gains and overall returns on mental health care investment.

In preliminary analyses of post-treatment data (n=194) in the current study in Kisumu, Kenya, non-specialist delivered IPT achieves MDD remission in 38% and PTSD remission in 52% of participants – greater than treatment as usual and higher than U.S. effectiveness studies (30%) with physician-delivered depression care. In a subsample with HIV viral load data (n=116), we have a nearly significant effect ($p=0.09$) on undetectability of HIV viral load (clinical goal): 82% of those in IPT have undetectable viral loads after their 12-week treatment, versus only 68% of those in usual care, despite the fact that all participants received usual HIV care, throughout.

Expertise and experience in training nurses in East Africa to administer fluoxetine for depression:

Our team has experience with training nurses and clinical officers to integrate with existing healthcare systems and successfully prescribe fluoxetine for depression, including HIV clinics in a neighbouring region of Uganda. In preliminary analyses of [name] and [name]'s INDEPTH study (n=415), 66% (n=272) completed a 9 month course of antidepressant therapy. Only 15% (n=61) had prematurely discontinued treatment —a higher rate of adherence than with SSRIs in High Income Countries (HICs). 78% of completers were in full remission at treatment conclusion and 66% in the intent to treat analysis, which classified those who prematurely discontinued treatment as non-responders. The majority of the treatment gains were achieved early in treatment (weeks 6-12), with a 68.5% average reduction on the Patient Health Question 9 item (PHQ-9) from baseline and little further gain with additional treatment.

Hypothesis and Specific Aims:

Aim 1:

Determine the effectiveness of non-specialist-delivered Interpersonal Psychotherapy (IPT), fluoxetine, or combination for MDD and PTSD.

Hypothesis 1a: Initial randomization to IPT or fluoxetine will have similar efficacy for post-treatment remission.

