Cost-benefit analyses. An important question for policymakers concerns the economic returns to investments in treating and improving mental health. We will use data obtained on the economic status of those treated to calculate the economic benefits associated with treated mental health disorders (both pooled analyses of IPT or fluoxetine treatment and separate analyses of IPT and fluoxetine treatment). We will also incorporate data on health care utilization and hospitalizations (Table 1). The value of these economic benefits will be summarized on a per-person basis and then combined with the implementation cost data to generate a rate of return on mental health expenditures (in general and by treatment type –IPT or fluoxetine). This rate of return is net gains in all economic measures divided by implementation costs, x 100 to yield % return. Cost and income measures will be adjusted for inflation and discounting during the 3 year study period.

Human participants in the project

Target population. Adult primary care outpatient clinic attendees at Kisumu County Hospital (KCH) and other Kisumu County Ministry of Health facilities.

Sample size calculations: SMART designs are used to inform the construction of optimal Adaptive Treatment Strategies (ATS), which is our goal. Therefore, we will power our study to detect the smallest difference between the various ATS included in the study design. The proposed SMART examines (1) first line treatment strategies with IPT or fluoxetine, including long-term relapse risk for participants who remit with initial treatment and (2) second line treatment strategies for non-remitters—specifically, treatment “switch” (from IPT to fluoxetine or vice versa) versus treatment “combination” (addition of IPT to fluoxetine or vice versa). Based on the current evidence base, we

expect that differences between switching or combining treatment will be smaller than other ATS comparisons in the study and we will therefore power the study to detect this difference.

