As it pertains to antidepressants and psychotherapy, the evidence base comparing “switching” versus “combining” treatment for non-remitters (second line treatment) is still developing. However, the field does have meta-analytic data on the differences between treating depression with antidepressants or psychotherapy alone, versus their combination. A 2009 meta-analysis (n=2036) which compared combination treatment (psychotherapy and pharmacotherapy) to pharmacotherapy alone for depression found an effect size of 0.31 (Cohen’s d).²⁷ A 2007 meta-analysis (n=903) found that the remission rate for major depression treated with psychotherapy and pharmacotherapy was better than psychotherapy alone, with an odds ratio of 1.5928, which when converted to a Cohen’s d is 0.25.²⁹ While specific studies have not yet been completed for IPT and PTSD, we leveraged the above-referenced meta-analyses of the effects of general psychotherapy and general pharmacotherapy to estimate sample size for the proposed study. Based on those studies, we would need approximately 164 per treatment arm to compare combined psychotherapy-medication treatment with medication alone, and 242 to compare combined psychotherapy-medication with psychotherapy, alone (using a two-sided alpha of 0.05 and power of 0.80). Using the conservative estimate, we will need 242 for each of the four treatment arms (968, total) after the second randomization (switch to fluoxetine, switch to IPT, combination after fluoxetine, combination after IPT). Note, this strategy uses fluoxetine treatment for 6 months as a first line treatment,

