consistent with the original R01 submission and responsive to reviewers' comments (summary statement response) on our funded U01 (DAPPER) study. While effectiveness data on treatment of depression in HICs (STAR*D) indicate that only approximately one-third remit with first line treatment, preliminary data from our current IPT study in Kisumu indicate remission rates over two-thirds. We will use a conservative estimate of the numbers entering the second randomization phase (non-remitters) and assume that half of study participants will need second-line treatment. Based on that estimate, the 968 participants randomized to the second stage of the SMART should represent 50% of those enrolled at the start of the trial, or 1936. Allowing for a 40% drop out rate across the 33 month duration of the study (domestic migration is common in Kenya³⁰), we will need 2710 participants for the SMART.

The additional number required for integration of the SMART design is 710 participants. Making a conservative assumption of ~20% prevalence of MDD and/or PTSD among primary care patients, we will screen 3,550 individuals to enroll 710 participants. While KCH and other Kisumu County Ministry of Health facilities see over 10,000 adult primary care patients per month, we will assume that only 20% of clinic attendees will undergo screening, and we will budget 3 months for recruitment. In order to avoid overwhelming mental health care providers, these 3 months of recruitment will be dispersed across a 18 month period: enrollment will halt when providers' caseloads are full and resume when at least 20% availability is regained. We will also work with Community Health Workers (CHWs) and Community Health Volunteers (CHVs) to

mobilize and sensitize the community about mental health services and refer community members to one of the health facilities for screening for the SMART-DAPPER study.

Eligibility criteria

Inclusion criteria:

- (1) KCH and other Kisumu County Ministry of Health facilities adult primary care outpatient clinic attendees who meet the threshold criteria for DSM-V for MDD and/or PTSD. .
- (3) Ability to attend weekly IPT sessions/fluoxetine monitoring in person or by telephone;
- (4) 18 years or older.

Exclusion criteria:

- (1) Cognitive dysfunction compromising ability to participate in IPT or accurately take fluoxetine (lack of orientation to person, place, time and situation);

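### The stated 80% power for second-line switch versus combination is at most 69% for remission if tested within each first-line arm, and the SAP does not say whether the test is within arm or pooled

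*Protocol*

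**What the plan says.** In the protocol's Sample size calculations, the aim is set out as "we will power our study to detect the smallest difference between the various ATS included in the study design". The sponsor expects that "differences between switching or combining treatment will be smaller than other ATS comparisons in the study", so switch versus combination sets the size of the trial.

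Two published effects feed the calculation. A 2009 meta-analysis comparing combination treatment "to pharmacotherapy alone for depression found an effect size of 0.31" (Cohen's d). A 2007 meta-analysis "found that the remission rate for major depression treated with psychotherapy and pharmacotherapy was better than psychotherapy alone"; its odds ratio is printed as 1.5928 and its converted d as 0.25. These give 164 per arm against medication alone, "and 242 to compare combined psychotherapy-medication with psychotherapy, alone (using a two-sided alpha of 0.05 and power of 0.80"). The larger is adopted: "we will need 242 for each of the four treatment arms (968, total) after the second randomization". The four arms are listed as switch to fluoxetine, switch to IPT, and combination after each first-line treatment. No test and no second-line remission rate are named.

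Remission is defined in the protocol (Study visits) as no longer meeting DSM-V threshold criteria, a yes/no outcome. The SAP's last paragraph compares switch with combination by Fisher's exact test for MDD or PTSD, and by an exact Wilcoxon test for BDI-2 or PCL-5. It does not mention first-line arm. The SAP calls the binary outcomes primary and the scores secondary for the first-line analysis.

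**The concern.** Each of the two sample sizes is tied to its own comparator (psychotherapy alone, medication alone) and then applied to four separate arms. That is the logic of a comparison within each first-line arm. The SAP's wording would equally fit one pooled comparison of all switched with all combined participants. Whether the stated 80% holds for remission depends on which is meant.

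The method adds a second problem. An odds ratio for a binary outcome was converted to a standardised mean difference, and the trial was sized as if that continuous measure would be analysed. A yes/no outcome carries less information than the continuous scale assumed in the conversion.

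At stake is the reading of a null result after first-line fluoxetine. Against a claimed 80%, it could be taken as fair evidence that combination adds little over switching to IPT. Against 55-69%, it could not.

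**Working it through.** **Inputs.** From the protocol: two-sided alpha 0.05, power 0.80, odds ratio 1.5928 as printed, d = 0.31, and 242 per arm in four arms. I read 1.5928 as 1.59 followed by a reference mark (an assumption; the literal value is also checked). The second-line comparator rate is not given and is varied. For orientation, the first-line figures are about one-third (high-income data), "preliminary data from our current IPT study in Kisumu indicate remission rates over two-thirds", and, in Preliminary studies, "IPT achieves MDD remission in 38% and PTSD remission in 52% of participants". Non-remitters may do worse than any of these.

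**Step 1: the plan's own figures.**
- d = ln(OR) x sqrt(3)/pi = 0.4637 x 0.5513 = 0.2557.
- n per arm = 2(1.960 + 0.842)^2/d^2 = 15.70/0.0654 = 240.1; with the t correction 241.1, so 242.
- The printed d = 0.25 gives 15.70/0.0625 = 251.2, that is 252, or 253 with the t correction. So 242 reproduces only from the unrounded d.
- d = 0.31 gives 163.3, or 164.3 with the t correction, against the stated 164.
- 4 x 242 = 968.

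**Step 2: where the power goes.** As a t-test, the expected z is 0.2557 x sqrt(242/2) = 0.2557 x 11 = 2.81, and Phi(2.81 - 1.96) is about 0.80. For a binary outcome the most favourable case has both rates near one half, where the standard error of the log odds ratio is about sqrt(8/n). The expected z is then 0.4637 x sqrt(242/8) = 0.4637 x 5.5 = 2.55, and Phi(2.55 - 1.96) is about 0.72.

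**Step 3: power on the remission scale.** With comparator rate p1, p2 = OR x p1/(1 - p1 + OR x p1). Chi-square power uses the usual two-proportion formula. Fisher power is a full enumeration of both binomials with the two-sided test at 0.05. OR 1.755 is exp(0.31 x pi/sqrt(3)).

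| Comparator rate | 242 v 242, OR 1.59, Fisher | 242 v 242, OR 1.59, chi-square | 242 v 242, OR 1.755, Fisher | 484 v 484, OR 1.59, Fisher |
|---|---|---|---|---|
| 20% | 54.6% | 58.3% | 72.9% | 85.1% |
| 30% | 64.8% | 68.0% | 82.1% | 92.0% |
| 38% | 67.8% | 71.3% | 84.4% | 93.7% |
| 45% | 69.1% | 72.0% | 84.9% | 94.2% |
| 60% | 64.4% | 67.7% | 80.4% | 91.9% |
| 67% | 59.2% | 62.7% | 75.4% | 88.6% |

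- OR 1.59 within arm: the maximum is 69.1% by Fisher and 72.0% by chi-square, both near a 44% comparator rate (44% v 55.5%). With the literal 1.5928 the maxima are 69.4% and 72.3%.
- OR 1.755 within arm: at least 80% by Fisher only at comparator rates of about 28-60%.
- OR 1.59 pooled, all 968 analysed: at least 80% at rates of 17-76%.

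**Step 4: detectable odds ratio.** At 242 v 242, 80% power by Fisher needs an odds ratio of 1.84 (at 20%), 1.73 (30%), 1.70 (38%), 1.69 (45%), 1.75 (60%) or 1.82 (67%).

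**Step 5: symptom scores.** With Wilcoxon efficiency 0.955 under a normal shift, 242 x 0.955 = 231 effective per arm. At d = 0.2557 this gives about 78% within arm.

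**Step 6: fewer analysable participants.** The protocol allows 40% drop-out over 33 months. If all of it fell before the second-line outcome and evenly across arms (an assumption), then 2710 x 0.6 = 1626; half is 813; a quarter of that is 203 per arm, or 406 per pooled group. Pooled Fisher power at OR 1.59 is then 78% at a 20% rate and 87-90% at 30-60%, and it is at least 80% only at about 22-69%. Within arm the maximum is about 62%.

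**The case against.** The best reply is that switch versus combination was always meant as one overall contrast, as the protocol's rationale and the SAP both phrase it. On that reading the stated power is exceeded at most plausible rates. This stands as a possibility, but neither document says pooled, and the four-arm sizing points the other way. Pooling also averages two different contrasts, one replacing or supplementing fluoxetine and one replacing or supplementing IPT, so it should be stated.

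The shortfall is narrow in other ways too. It affects one of the two pairs fully, and the other only outside comparator rates of 28-60%. The sample size text names no outcome, one of its inputs was reported as a d, and the symptom scores have close to the planned power. All of that stands. It does not rescue the remission figure, because the effect that set the 242 was a remission odds ratio and the SAP tests a binary outcome.

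A reader might infer that t-test sizing alone explains the fall to 69%. It does not: it accounts for about 8 points (80% to 72%), and Fisher's conservatism for about 3 more. A reader might also infer that pooling removes the problem outright. That holds only over a range of comparator rates, which narrows if fewer than 968 are analysed.

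**Conclusion.** The 80% is not delivered for remission on the within-arm comparison that the protocol sizes. For combination versus psychotherapy alone after fluoxetine, at an odds ratio of 1.59, power is at most 69% by the SAP's test, and 55-69% over comparator rates of 20-67%. The ceiling needs no assumption about remission rates; the point values do. It rests on the within-arm reading and on 242 analysed per arm.

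The documents do not support the stronger conclusion that the second stage as a whole is underpowered or that the trial must enrol more. The practical shift is modest: a detectable odds ratio of about 1.70-1.75 instead of 1.59 at comparator rates of 30-60%, and about 1.8 at 20% or 67%. What should be corrected is an unspecified comparison and a power statement that does not match the planned test.

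**What to change.** 1. State in the SAP whether switch versus combination is tested within each first-line arm or pooled across them. The SAP is written in the past tense; if this analysis has been run, record which comparison was made and when that was decided.
2. In the protocol's sample size section, replace the 80% figure with power on the remission scale for that choice, giving the assumed comparator rate and the analysable number. Within arm: at most 69% for an odds ratio of 1.59, or 80% for a detectable odds ratio of about 1.70-1.75 at rates of 30-60%. Pooled: at least 80% for 1.59 at rates of 17-76% if all 968 are analysed, or about 22-69% at 406 per group. Say also that the 242 uses d = 0.2557, not the printed 0.25.

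The cost is two or three sentences. No enrolment, treatment or test needs to change. If the within-arm reading is chosen, the sponsor accepts a less favourable power figure for the pair after fluoxetine.

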Retention: Based on previous work, retention is not expected to be a problem. Our pilot study of IPT for Sudanese refugees in Cairo had a 93% retention rate; our study of IPT for survivors of the Sichuan earthquake had an 85% retention rate and our ongoing study of integrated IPT care with HIV+GBV+ women in Kisumu has 300 enrollees with 20 dropouts (93% retention, to date). However, given uncertainty regarding generalizability to the KCH and other Kisumu County Ministry of Health facilities adult primary care clinics, the more conservative estimate of 20% drop-out will be used. However, provision of treatment over the telephone may improve retention rates. As part of retention efforts, participants will be asked to provide the name and phone number of a trusted adult who can be contacted if the study has concerns about participants' welfare or whereabouts. Therapists and fluoxetine providers will be asked to provide study cell phone numbers to study participants. Missed appointments will be followed with at least two efforts to reach the participant directly and/or through their contact (80% cell phone coverage). Likewise, at least two efforts will be made to reach drop-out participants for remaining measures.

Acute mental health care: IPT therapist and fluoxetine training will include risk assessment and referral procedures for acute mental health care needs. See Protection of Human Subjects section for details.

Clinical evaluators: Clinical evaluators will be blind to treatment group and will conduct baseline screening at the primary care clinic prior to initiating treatment, as well as re-assessments at months 1.5 (mid-treatment for IPT), 3 (mid-treatment for fluoxetine), 6, 9 month 12, 18, 24 and 30. Candidate clinical evaluators will undergo a two day training during which they will be introduced to the study measures and their proper application. At the conclusion of the training, the candidates will be observed in their administration of the measures, assessing for accuracy and completeness. If successful, they will be evaluated for reliability by conducting a group interview and comparing measure results. Those who demonstrate both accuracy and inter-rater reliability will be invited to join the study. Monetary compensation will be provided for completed measures at the local currency equivalent of 7usd.

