Concept Mapping. We will use the IRT and extended IRT members to inform study related implementation questions using concept mapping methods. Concept Mapping is a process that allows stakeholders to express their ideas on a given topic, examine how these ideas relate to one another, and determine what ideas are judged to be most important or critical for a particular goal or initiative. Concept Mapping has three activities all to be completed online: 1) begins with a brainstorming process in which participants respond to a focus statement, 2) each participant is provided with a complete set of the statements and asked to sort them into categories based on similarity, and 3) each participant will rate statements.

Feasibility. Attrition from the study will be evaluated in regards to both timing (active treatment or follow-up phase) and reason (e.g., symptom remission, move out of the region, lost wages/dependent care, cost/burden of transport, displeased with treatment). With the exception of those who leave the study because their symptoms remit (“cured”), the IPT/fluoxetine will be considered feasible if fewer than 20% of participants leave during treatment and if one or fewer therapists/fluoxetine provider voluntarily leave the study.

Fidelity

Therapist Adherence to IPT Protocol. Therapists will discuss each IPT session with a supervising clinician. During supervision, therapists will be assisted with their adherence to and application of IPT. Adherence will be scored using a 10 point Likert scale assessing adherence in each IPT phase (used in our current IPT study). Sessions will be

considered adherent to the IPT protocol if they average a score of 5 or higher and do not employ off-protocol interventions. All sessions will be audio-taped and 20% of sessions will be selected using blocked randomization to ensure both early and late sessions are included, then transcribed and translated for IPT adherence scoring by an independent rater.

Fluoxetine Provider Adherence to Fluoxetine Protocol. In collaboration with the study coordinators, Drs. [name] and [name] (co-Is) will randomly select 10 charts of treated patients each month to assess compliance with the fluoxetine treatment protocol (eligibility, dosing and monitoring of side effects). Treatment will be considered adherent if there are no deviations from protocol.

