Project Title: SMART-DAPPER: Leveraging the Depression And Primary-care Partnership for Effectiveness-implementation Research Project (SMART-DAPPER)

Clinicaltrials.gov number: NCT03466346

Title of Document: Statistical Analysis Plan

Date of Document: October 27, 2021

Statistical Analysis Plan

We used an intent-to-treat analysis. We used multivariate normal multiple imputation with 100 imputations to impute missing values of BDI-2 and PCL-5. For both of our primary outcomes (binary) we used generalized estimating equations (GEE) methods to fit a log-link binomial regression model with robust standard errors and a working exchangeable correlation structure to accommodate the repeated measures over time. Because not all participants had both major depression and PTSD at baseline, our analysis models the change in the risk of the outcome from baseline to end of first-line treatment.

Correspondingly, our model included the predictors of time (e.g., baseline and end of treatment), intervention group, the interaction of time, and intervention group. Results are described in terms of relative risks, and, for the interaction, ratios of relative risks with corresponding confidence intervals. The primary test of interest is the time by group interaction.

Secondary outcomes (BDI-2, PCL-5 continuous scores) were numeric, continuous variables. For these analyses we used GEE methods to fit a linear regression model with robust standard errors and a working exchangeable correlation structure. As before, our model included the predictors of time (baseline, end of treatment), intervention group and the interaction of time and intervention group. Results are described in terms of differences in mean values and, for the interaction, differences of differences with corresponding confidence intervals. The primary test of interest is the time by group interaction.

Participants who were not in remission at end of first line treatment were re-randomized to either treatment switch or treatment combination. These randomized comparisons were conducted using Fisher's exact test for MDD or PTSD or an exact Wilcoxon rank-sum test for BDI-2 score or PCL-5 score.

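### The enrolment of 2710 allows for 28.6% loss, not the 40% stated, and no drop-out rate is tied to the second-stage endpoint that sized the trial

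*Protocol*

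**What the plan says.** The protocol's Sample size calculations section powers the study on second-line switching versus combination, the comparison it expects to show the smallest difference. From two meta-analytic effects it derives 164 per arm (combination versus medication alone, d = 0.31) and 242 per arm (combination versus psychotherapy alone, odds ratio 1.59, d about 0.25). It adopts the larger: "Using the conservative estimate, we will need 242 for each of the four treatment arms (968, total) after the second randomization". Assuming that half of participants will not remit, it takes 968 as half of 1936. The last step reads "Allowing for a 40% drop out rate across the 33 month duration of the study", followed by "we will need 2710 participants for the SMART".

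Two other places give a drop-out figure. Under Retention, "the more conservative estimate of 20% drop-out will be used", with no period named. Under Feasibility, treatment "will be considered feasible if fewer than 20% of participants leave during treatment". The SAP says of the second stage: "These randomized comparisons were conducted using Fisher's exact test for MDD or PTSD", with an exact Wilcoxon rank-sum test for the BDI-2 and PCL-5 scores. It names no assessment month and does not say whether the two first-line groups are pooled.

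The remission figures behind the 50% also vary. For first-line treatment in high-income countries, the data "indicate that only approximately one-third remit with first line treatment". The sample size section puts remission in the team's current Kisumu IPT study above two-thirds, whereas Preliminary studies gives 38% (MDD) and 52% (PTSD) for it. For fluoxetine in Uganda, "78% of completers were in full remission at treatment conclusion and 66% in the intent to treat analysis".

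**The concern.** A drop-out rate is a fraction of those enrolled, so the allowance should divide by the retained fraction. Multiplying by one plus the rate gives too small a number, and the gap widens as the rate rises. A reader will take 242 per arm to survive 40% attrition, which it does not.

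The loss that matters here is the loss by the second-stage assessment. The documents do not give it: one rate spans the whole study, one has no period, and one is a benchmark for leaving during treatment. The power of the comparison that determined enrolment therefore cannot be read from the plan. A null switch-versus-combination result could be over-interpreted by someone relying on the stated allowance.

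**Working it through.** **Reproducing the plan's figures** (two-sided alpha 0.05, power 0.80)

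- d = ln(1.59) x sqrt(3)/pi = 0.2557. A two-sample t-test needs 241-242 per arm, matching 242. Rounding to d = 0.25 would give 252-253, so 242 comes from the less rounded effect and is not an error.
- d = 0.31 needs 164-165 per arm, matching 164.
- 242 x 4 = 968; 968/0.50 = 1936.
- 1936 x 1.40 = 2710.4, matching 2710. The alternatives do not match: 1936/0.60 = 3226.7; 1936/0.80 = 2420; 1936 x 1.20 = 2323.2.

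**What 2710 covers.** The addition is 2710 - 1936 = 774. That is 40% of 1936 but 774/2710 = 28.6% of those enrolled. A 40% loss leaves 2710 x 0.60 = 1626, and keeping 1936 would take 3227, or 517 more.

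**Loss by the second-stage endpoint.** If second courses last as long as first courses (assumption), the second stage ends at about months 9-12. If 40% over 33 months accrues steadily (assumption), loss by month t is 0.40 x t/33 (linear) or 1 - 0.6^(t/33) (constant hazard). This gives 10.9-13.0% at month 9 and 14.5-17.0% at month 12. Loss reaches 28.6% only at months 21.7-23.6.

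**Second-stage n and power.** n per arm = 2710 x (1 - loss) x (1 - remission)/4, assuming equal splits and loss unrelated to remission. The table is for fluoxetine-first participants (combination versus switch to IPT), the contrast that set 242. The t-test range covers d = 0.25 to 0.256. Fisher power is exact, for odds ratio 1.59 with comparator remission of 30-60% (assumption).

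| Loss by endpoint | First-line remission | n per arm | t-test power | Fisher power |
|---|---|---|---|---|
| 14.5-17.0% | one-third | 375-386 | 93-94% | 84-88% |
| 14.5-17.0% | 50% | 281-290 | 84-87% | 71-77% |
| 14.5-17.0% | 66% | 191-197 | 68-72% | 53-58% |
| 20% | one-third | 361 | 92-93% | 82-85% |
| 20% | 50% | 271 | 83-84% | 70-74% |
| 20% | 66% | 184 | 67-69% | 52-57% |
| 28.6% | 50% | 242 | 78-80% | 64-69% |
| 40% | one-third | 271 | 83-84% | 70-74% |
| 40% | 50% | 203 | 71-73% | 57-61% |
| 40% | 66% | 138 | 54-56% | 40-42% |

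Non-remission needed to keep 242 per arm is 968/(2710 x (1 - loss)): 42-43% at 14.5-17.0% loss, 44.6% at 20%, 50% at 28.6% and 59.5% at 40%. Fisher's test needs about 314-343 per arm for 80% power at odds ratio 1.59, whatever the loss.

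**IPT-first contrast** (combination versus switch to fluoxetine; d = 0.31, 164 needed). At remission of 38%, 52% and two-thirds, 40% loss leaves 252, 195 and 135 per arm, with t-test power of 93%, 86% and 72%. A 20% loss leaves 336, 260 and 181, with power of 98%, 94% and 84%.

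**If first-line groups are pooled**, 40% loss and 50% remission leave 406 per group. At the smaller effect, t-test power is 94-95% and Fisher power 87-90%.

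**The case against.** The strongest reply is that no shortfall follows at the protocol's own 50% non-remission. The 40% is a whole-study figure, and on steady accrual the second-stage loss is well under 28.6%. Even spread over the 30-month follow-up given in the Abstract, month-12 loss is only 16.0-18.5%. At 20% loss, 271 per arm remain. This stands as an argument about consequences, but it rests on an accrual pattern the documents do not give.

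The IPT-first contrast is also well covered. At 50% non-remission, 2710 keeps 164 per arm up to 1 - (164 x 8)/2710 = 51.6% loss, and 203 per arm gives about 88% t-test power at d = 0.31. This is correct. The protocol, however, asks for 242 in every arm, and that target is protected only to 28.6%.

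The low cells combine unlikely inputs: all the 33-month loss falling before the second-stage endpoint, and 66% remission taken from HIV clinics in Uganda with a nine-month course. That 66% is itself hard to reconstruct (78% of 272 completers is 212, or 51% of 415). These cells are bounds, not forecasts.

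The Fisher deficit comes from the choice of test, not from the drop-out formula. For the BDI-2 and PCL-5 scores, the SAP's Wilcoxon test would have about 82-85% power at 281-290 per arm under normality. Both points are fair. They support stating power for each planned test.

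The 20% and 40% rates may simply cover different periods, so they are not shown to contradict each other. That stands; the gap is that the periods are not stated.

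**Conclusion.** The stated allowance is wrong as written: 2710 covers 28.6% loss, and a true 40% would need 3227. This follows from the protocol's own figures without any assumption. Whether second-stage power suffers is open, because it depends on loss by an endpoint for which no loss is given, and on first-line remission. At 50% remission, t-test power for the contrast that set 242 runs from 71-73% (all 40% lost by then) to 84-87% (steady accrual to month 12), against 80% planned. Fisher power is lower throughout, under the assumed comparator remission.

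A secondary point is that the 50% non-remission assumption is described as conservative. It is so against one-third or 38% remission, but not against two-thirds or 66%, since higher remission leaves fewer to re-randomise. The first-line time-by-group analysis in the SAP is not affected.

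**What to change.** Enrolment can stay at 2710. In the protocol:

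- State that 2710 allows for 28.6% loss, not 40%.
- State the period to which the 20% and the 40% each apply, and the loss expected by the second-stage endpoint.
- Restate second-stage n and power at that loss for each contrast, over the cited remission rates (fluoxetine-first: one-third to 66%; IPT-first: 38%, 52% and two-thirds). Do this for the SAP's Fisher's exact test as well as the t-test on d, and say whether first-line groups are pooled.
- Secondary: reconcile the two accounts of remission in the Kisumu IPT study, and either justify calling the 50% conservative or drop the word.

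The cost is wording and a short power table. Design, enrolment and primary analysis do not change, though stated second-stage power may look less favourable, depending on the loss and remission adopted.
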